2. T=6 hrs (+/- 4 hrs)
3. T=12 hrs (+/- 4 hrs)
4. T=24 hrs (+/- 4 hrs)

Data Collection:

Cytokine and biomarker analysis: Blood will be processed, aliquoted and frozen at -80°C for later cytokine and potential other biomarker analyses. Measurements will include but not necessarily be limited to Interleukin (IL)-1 β , IL-6, IL-8, IL-10, metabolomic profile, CRP, procalcitonin, and IL-6, IL-4, IL-10, TNF alpha at serial time points (0, 6, 12, 24 hours) after study drug delivery. The inflammatory cascade assays will be measured in the Center for Resuscitation Science Laboratory.

Oxygen metabolism analysis: Research blood will be used in the isolation of peripheral blood mononuclear cells (PBMCs) from blood: Plasma will be separated by centrifugation at 800g for 15min at 4°C and saved without disturbing the buffy coat. Then plasma will be replaced with the same volume of phosphate buffered saline (PBS). The cell pellets will then be mixed by gently pipetting up and down several times to disperse the cells. Next, PBMCs will be isolated from the PBS substitute blood samples using density gradient, Ficoll-Paque premium (GE Healthcare Bio-Sciences Corp).

The isolated PBMCs will be used in the cellular metabolism and mitochondrial function analysis. Using the XF24 Extracellular Flux Analyzer (Seahorse Bioscience) we will simultaneously measure the oxygen consumption rate (an indicator of mitochondrial respiration), and the extracellular acidification rate (an indicator of the lactate produced e.g. anaerobic metabolism). First, PBMCs will be re-suspended in Dulbecco's modified Eagle's medium and seeded in a 24-well assay plate pre-coated with CellTak (BD Biosciences) and incubated at 37°C for 30 min to allow cells to attach to the bottom of the plate. Then the wells will be washed and 675uL of fresh XF assay buffer will be added to each well. The plate will be incubated at 37°C without Carbon Dioxide (CO₂) for 1 hour prior to assay start.

Lactate, ScVO₂ measurements: Lactate and ScVO₂ levels will be measured using whole blood collected in a standard blood gas syringe by the clinical nursing team with the assistance of our research staff at the bedside prior to drug delivery (baseline), and again at 0, 6, 12, 24 hours after enrollment. The sample will be sent to the hospital's clinical lab for immediate analysis.

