Additional hemodynamic endpoints: While the primary endpoint will be difference in norepinephrine dose at 6h, we will also measure the difference in vasopressor dose between groups at 12h and over time using mixed linear model (see data analysis). We will also measure differences in heart rate at the 6 and 12h time points and over time (see data analysis). Other secondary hemodynamic endpoints will include time to shock reversal (cessation of all vasopressors for at least 12h) and change in lactate over time (0, 6, 12, 24 h).

Oxygen consumption: Aim #2a endpoint will consist of difference in oxygen consumption over time between esmolol and control groups. Based on findings in the Morelli *et al.* study, we anticipate a similar decrease in VO_2 among those who receive esmolol. While Morelli *et al.* measured VO_2 via PA catheter, we will measure VO_2 directly via the ventilator.

Inflammatory endpoints: For Aim #2b, we will characterize the effects of esmolol infusion on the inflammatory cascade as measured by changes in select inflammatory biomarkers at time points 12 and 24 hours accounting for baseline measurements at time zero.

Clinical endpoints: Recognizing that we lack power to detect differences in mortality, we will still collect in-hospital mortality anticipating that if the overall study is positive, we can use these data to help power a future Phase III trial. In addition, we will measure the clinical endpoints of length of ICU stay, hospital length of stay, and organ dysfunction at 96 hours as defined with the SOFA score.

Data acquisition and management: [name] and the Center for Resuscitation Science have extensive experience in data collection, data entry, database development, and data management for both large-scale observational trials and randomized clinical trials. The Center for Resuscitation Science currently manages over 20

active databases with over 1 million data points from nearly 10 years of research. As such, we have honed an effective and reliable protocol for managing data as described below.

Data Entry and Quality:

Immediately following data collection, the paper data sheet will be entered directly into the electronic database REDCap (described below). Two trained research assistants will independently enter the data for primary and secondary endpoints to ensure transfer accuracy. Several measures are taken to assure data quality. They are as follows:

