from the time of study drug administration over a period of at least 24 hours) between groups using mixed linear model accounting for repeated measures (n = 15). We did not adjust for pre-intervention VO₂ measurements. Using this model, we tested for mean differences at 12 hours, 24 hours and for differences in the overall trend over time. The appropriate variance-covariance structure was selected based on Akaike information criterion. Additionally, a figure was created by first computing the mean of all the VO₂ observations for a patient by timepoint, and then computing the mean of the means for each timepoint by treatment group.

To characterize effects of esmolol on inflammatory markers in patients with vasopressor-dependent septic shock, we compared log-transformed values of biomarkers at 12 and 24 hours and over time between groups using mixed linear model accounting for repeated measures and adjusting for pre-intervention biomarkers. The appropriate variance-covariance structure was selected based on Akaike information criterion.

In-hospital mortality was compared between groups using the Fisher's Exact test. Baseline covariates appeared to be balanced, so we did not adjust for any additional covariates. Length of hospital and ICU stay was compared between groups using a Wilcoxon ranked sum test and stratified based on hospital survival. To characterize effects of esmolol on SOFA score over the first 24 hours, we compared SOFA at 6, 12, and 24 hours and over time between groups using a mixed linear model accounting for repeated measures and adjusting for pre-intervention SOFA.

All analyses were conducted using Stata 14.2 (College Station, TX) and a p-value of <0.05 was considered significant.

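### Three unadjusted 0.05 tests per biomarker give roughly a 40–70% chance of at least one false-significant result, in either direction, if esmolol affects none of the eight named markers

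*SAP*

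**What the plan says.** The last sentence of the SAP sets the threshold for every analysis: "a p-value of <0.05 was considered significant". For the inflammatory markers, the SAP states that "we compared log-transformed values of biomarkers at 12 and 24 hours and over time between groups", using a mixed model adjusted for the pre-intervention value. That is three contrasts per marker. The SAP does not say which markers.

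The list is in the protocol (B3.A, Data Collection, Cytokine and biomarker analysis). It opens with "Measurements will include but not necessarily be limited to" and, after IL-1β, continues with "IL-6, IL-8, IL-10, metabolomic profile, CRP, procalcitonin, and IL-6, IL-4, IL-10, TNF alpha at serial time points". IL-6 and IL-10 appear twice, which leaves eight distinct analytes: IL-1β, IL-4, IL-6, IL-8, IL-10, TNF-α, CRP and procalcitonin. There is also a metabolomic profile of unstated size.

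The protocol's endpoint for Aim 2b (B3.A, Secondary endpoints, Inflammatory endpoints) is narrower: "changes in select inflammatory biomarkers at time points 12 and 24 hours accounting for baseline measurements at time zero". That is two contrasts, and the selection is not made there or elsewhere in the supplied text. Specific Aim #2b in B1 is worded as the test of a hypothesis that esmolol modifies the inflammatory response.

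**The concern.** A per-test rule of 0.05 does not limit the error rate of an aim that is assessed by many tests. Here the number of tests is not fixed: the SAP names no markers, the protocol's list is open, and the SAP adds a contrast to the two in the protocol. The supplied text contains no lead marker, no adjustment, no exploratory label and no commitment to report every analyte assayed.

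The stake is how Aim 2b will be read. It is a named aim in hypothesis-testing language, and the trial is meant to inform a Phase III design. One marker below 0.05 at one time point could be reported as a significant effect on inflammation, and the reader could not tell how many tests it came from.

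**Working it through.** **Inputs.** The per-test threshold of 0.05 is from the SAP's last sentence; sidedness is not stated, and two-sided is assumed. The eight markers are from the protocol's biomarker list, and the three contrasts are from the SAP. The correlations are assumptions, because the documents give none. All probabilities below suppose that esmolol affects none of the eight markers.

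**Step 1: the plan's own figure.** The documents state no error rate for Aim 2b. The only related figure is the total of 104 for the primary comparison (difference 0.05, SD 0.09, power 80%). The normal formula gives n per arm = 2(1.960 + 0.842)² × 0.09²/0.05² = 2 × 7.85 × 3.24 = 50.9, so 51. The exact t-test gives 51.84, so 52 per arm, a total of 104, with power 0.801. The figure reproduces. The power calculation therefore covers the primary comparison and nothing else.

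**Step 2: test count and expected false positives.** 8 × 3 = 24 tests. Expected false positives are 24 × 0.05 = 1.2 whatever the correlation. By symmetry, 24 × 0.025 = 0.6 of these fall in the anti-inflammatory direction.

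**Step 3: independent tests.**
- Either direction: 1 − 0.95²⁴ = 0.708.
- Anti-inflammatory direction: 1 − 0.975²⁴ = 0.455.
- Independent tests needed to pass one half: ln 0.5/ln 0.95 = 13.5, so 14, in either direction; ln 0.5/ln 0.975 = 27.4, so 28, in the favourable direction.

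**Step 4: correlated tests.** The three contrasts on a marker come from one repeated-measures model, and the markers belong to one inflammatory cascade, so independence is an upper-end case. A simulation with no effect on any marker used 60,000 replicates per setting and eight markers. The contrasts were at 12 hours, at 24 hours and over time, the last tested either as a linear slope or as a 2-df group-by-time test over 6, 12 and 24 hours. Within-marker correlation ran from 0 to 0.9.

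| Assumed between-marker correlation | At least one p<0.05, either direction | At least one, anti-inflammatory direction |
|---|---|---|
| 0 | 0.62–0.67 | 0.37–0.42 |
| 0.3 | 0.57–0.61 | 0.32–0.35 |
| 0.5 | 0.49–0.54 | 0.26–0.29 |
| 0.7 | 0.39–0.43 | 0.20–0.23 |

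With step 3 as the upper end, the ranges are 0.39–0.71 in either direction and 0.20–0.46 in the anti-inflammatory direction. Each marker was given one favourable direction, which is a simplification: the documents do not define it.

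**Step 5: the protocol's two contrasts only.** 8 × 2 = 16 tests. Under independence, 1 − 0.95¹⁶ = 0.560 in either direction. Across the simulated settings the range is 0.25–0.56 in either direction and 0.12–0.34 in the favourable direction.

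**Step 6: scale of a correction.** Bonferroni over 24 tests would need 0.05/24 = 0.0021 per test. Benjamini-Hochberg compares the smallest of 24 p-values with that same figure and relaxes the bar for the ones after it. If no marker is affected, every rejection is false, so a 5% false discovery rate also holds the chance of any claim to 5%, under independence or positive dependence.

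**The case against.** The strongest reply is that this is a Phase II pilot with its hierarchy already written. The protocol names one primary endpoint, the SAP powers only that one, and Aim 2b sits under secondary endpoints. Formal error control for mechanistic markers in a pilot is partly a matter of taste. The count of 24 is also inferred: the eight markers come from a laboratory section, and the third contrast is only in the SAP. These points stand as limits on severity. They do not remove the problem, because Aim 2b is worded as a hypothesis test, the SAP applies the same word, significant, to all results, and even two contrasts per marker give at least 25% in either direction.

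Three stronger readings are tempting, and the documents do not support them.

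- *Aim 2b is more likely than not to report a false anti-inflammatory effect.* The 71% counts both directions and assumes independence. In the favourable direction the figure is 45.5% under independence and lower with correlation. Even in either direction it is about 40% at a between-marker correlation of 0.7. More markers or metabolomic features could raise these figures, but the documents give no number.
- *A false positive somewhere among the secondary results is 90% likely.* Counting NED 2, heart rate 3, lactate 3, shock-free days 1, VO₂ 3, biomarkers 24, mortality 1, length of stay 4 and SOFA 4 gives 45 tests, and 1 − 0.95⁴⁵ = 0.90. That holds only if all 45 are independent, and many are repeated measures on the same patients.
- *The report cannot separate the powered test from the rest.* It can, since the primary endpoint and its sample size are explicit. What is missing is the exploratory label.

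The finding of absence is also limited. The protocol's secondary endpoints refer to a data analysis section that is not in the supplied text.

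**Conclusion.** The concern holds for the supplied text. Followed as written, the SAP gives 1.2 expected false-positive biomarker tests. The chance of at least one is roughly 40–70% in either direction, and about 20–45% in the anti-inflammatory direction. The either-direction figure is relevant because Aim 2b is stated without direction and no passage says which change in each marker would count as support.

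The figures rest on eight markers, three contrasts, two-sided tests, no effect of esmolol on any of the eight, and assumed correlations of 0 to 0.7 between markers and 0 to 0.9 within a marker. The primary 6-hour comparison and its error rate are not affected. The plan should be changed on this point, but it does not threaten the main conclusion.

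**What to change.** Replace the last sentence of the SAP with text to this effect:

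> A confirmatory claim at two-sided 0.05 is made for the 6-hour NED comparison only. The biomarker tests (every analyte assayed; 12-hour, 24-hour and over-time contrasts) form one family, reported with Benjamini-Hochberg adjusted p-values at a 5% false discovery rate. Every analyte assayed is named and reported, with the number of tests in the family. Biomarker and other secondary results are exploratory and given with 95% confidence intervals.

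The adjustment is confined to the biomarkers. For the other secondary endpoints the label and intervals are enough.

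The cost is one changed passage and one column of adjusted p-values, with no new data. Some biomarker p-values will look less favourable. The SAP is dated December 3, 2020 and already reports observed facts, such as no deaths before 6 hours and 15 patients in the VO₂ analysis. It should therefore say that the adjustment was added after data were seen. For the same reason, naming a lead marker now would carry little weight; full reporting of what was assayed is the better safeguard.
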